5.3.4 Subjective Posterior Capsule Opacification (PCO) Assessment

The number and percentage of eyes representing the maximum rating for an eye during the study will be tabulated by the response categories presented on the CRF (i.e., none, clinically nonsignificant, clinically significant, clinically significant requiring a YAG) and summarized by treatment. Similarly, eyes with a ‘worst case’ rating of clinically significant PCO or posterior capsulotomy (YAG) will be summarized by the response categories on the CRF. The summaries described above will also be further summarized by toric and non-toric lenses, for all eyes combined only.

A listing of eyes with clinically significant PCO, clinically significant PCO requiring YAG, or posterior capsulotomy will be presented which includes the PCO or capsulotomy results at all visits. The listing will include, but are not limited to, the following variables: treatment, IOL model, subject identification number, age, sex, surgery eye (first or second implanted eye), eye (OD or OS), visit, days from surgery, and PCO or capsulotomy details at each visit.

5.3.5 Posterior Capsulotomy

The number and percentage of eyes with posterior capsulotomy (overall and by reason) will be tabulated by treatment.

Posterior capsulotomy will also be summarized by toric and non-toric lenses for all eyes combined only.

5.3.6 Surgical Problems

The number and percentage of eyes with surgical problems as per the CRF (e.g., anterior capsular tear) will be presented by treatment. In addition, a listing of subjects with surgical problems will be provided. The listing will include the following variables: treatment, subject identification number, age, sex, surgery eye (first or second implanted eye), eye (OD or OS), and description of surgical problem.

Surgical problems will also be summarized by toric and non-toric lenses for all eyes combined only.

5.3.7 Other Procedures at Surgery

A listing of all other surgical procedures will be provided. The listing will include the following variables: treatment, subject identification number, age, sex, surgery eye (first or second implanted eye), eye (OD or OS), and type of other surgical procedure.

5.3.8 Slit Lamp Examination

For each slit lamp parameter as per the CRF, numbers and percentages of eyes that experience an abnormality at each scheduled visit will be presented by treatment.

A listing will be provided which presents all eyes with an abnormality in any slit-lamp parameter at any postoperative visit. The listing will include all slit-lamp data from all visits with the following variables: treatment, subject identification number, age, sex, surgery eye (first or second implanted eye), eye (OD or OS), visit, days from surgery, and slit lamp parameter.

Slit lamp abnormalities will also be summarized by toric and non-toric lenses for all eyes combined only.

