It is recommended that Visit 00 (1st eye surgery) occur within 0 to 30 calendar days after the Preoperative Visit (Visit 0). It is allowable for the 2nd eye to be operated on the same day as the 1st eye per the investigator's medical judgement. It is recommended that the 2nd eye surgery occur no longer than 14 days after the 1st eye surgery. **Note:** If a subject must re-schedule 1st eye surgery (Visit 00) and the date exceeds 60 days from Visit 0, the subject may continue study participation if Visit 0 biometry, tonometry, slit lamp examination, and dilated fundus exam assessments are repeated and occur within 60 days of the rescheduled surgery, and the subject is confirmed to continue to meet all entry criteria.

A total of up to 7 scheduled visits are planned: the Screening/Visit 0 and two Operative Visits (Visit 00 and Visit 00A), Visit 1, Visit 1A, Visit 2A and Visit 3A. Postoperative visits must occur at the following intervals: Visit 1/1A (Days 1-2) after 1st and 2nd eye surgery respectively, Visit 2A (Days 30-60) after the 2nd eye surgery, and Visit 3A (Days 90-120) after the 2nd eye surgery.

Figure 7-1 Study Diagram

* Option for the 2nd eye to be operated on the same day as the 1st eye. It is recommended that Visit 00 (1st eye surgery) occur within 0 to 30 calendar days after the Preoperative Visit (Visit 0). If not occurring on the same day, the 2nd eye IOL implantation should be conducted within 14 days after 1st eye implantation.

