12.6 Safety Analyses

The safety endpoints are:

- All adverse events (ocular and non-ocular, serious and non-serious)
- SSI
- Device Deficiencies
- IOL observations
- IOL position change (tilt and decentration)

- PCO
- Posterior capsulotomy
- Surgical problems
- Other surgical procedures
- Slit lamp examination
- Dilated fundus examination
- IOP

There are no safety hypotheses for this study. For all safety measures, descriptive statistics generated will be based upon the type of variable. For categorical variables summary statistics will include sample size, number in category, and % in each category. For continuous variables, number of subjects/eyes, mean, median, standard deviation, minimum, and maximum will be reported.

All adverse events occurring from the time a subject sign informed consent to study exit will be accounted for in the reporting. Safety analyses will be conducted using the safety analysis set on a treatment-emergent basis. Descriptive summaries (counts and percentages) and listings will be presented. Individual subject listings will be provided for AEs that occur after signing informed consent but prior to exposure to IP.

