5.3 Statistical Methods for Safety Analyses

Except otherwise stated, the analysis set for all safety analyses is the SAS as defined in Section 2.2. Baseline will be defined as the last measurement prior to exposure to investigational product, except otherwise stated.

Unless otherwise specified, all eye-level safety endpoints will be summarized by treatment, separately for first implanted eyes and second implanted eyes, as well as for all eyes combined. When combining eyes, mixed effects models will be utilized to account for the correlation between subject-eyes when estimating confidence intervals.

In addition to the analyses presented below a listing of all monocular BCDVA for eyes with a loss of 10 letters or more at 3 months compared to 1 month will be provided; where a 10 letter loss (decrease) is a change in BCDVA of at least 0.2 logMAR.

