5.3.9 Dilated Fundus Examination

For each dilated fundus parameter as per the CRF, numbers and percentages of eyes that experience abnormality at each scheduled visit will be presented by treatment.

A listing will be provided which presents all eyes with an abnormality in any fundus parameter at any postoperative visit. The listing will include all fundus examination data from all visits with the following variables: treatment, subject identification number, age, sex, surgery eye (first or second implanted eye), eye (OD or OS), visit, days from surgery, and fundus parameter.

Dilated fundus abnormalities will also be summarized by toric and non-toric lenses for all eyes combined only.

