5.3.10 Intraocular Pressure

Intraocular pressure (IOP) measurements will be recorded in mmHg and rounded to the nearest whole mmHg. All analyses will be presented by treatment.

Descriptive statistics (number of eyes, mean, median, SD, minimum, maximum, and two-sided 95% confidence interval) of observed values and change from baseline values will be presented at each study visit.

A listing will be provided which presents all eyes with an increase or decrease in IOP of more than 10 mmHg at any postoperative visit compared to the same eye at baseline. The listing will include the following variables: treatment, IOL model, subject identification number, age, sex, surgery eye (first or second implanted eye), eye (OD or OS), visit, days from surgery, value at the visit, baseline value, and a change from baseline value.

IOP will also be summarized by toric and non-toric lenses for all eyes combined only.

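### The by-visit slit-lamp and fundus tables do not separate new or worsened abnormalities from those already present before surgery

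*SAP*

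**What the plan says.** For each slit-lamp parameter on the case report form, SAP 5.3.8 states that "numbers and percentages of eyes that experience an abnormality at each scheduled visit will be presented by treatment". SAP 5.3.9 says of each fundus parameter that "numbers and percentages of eyes that experience abnormality at each scheduled visit will be presented by treatment". Neither section mentions baseline status, a shift from Visit 0, or new or worsened findings in these tables.

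Both sections add a listing of eyes that are abnormal at any postoperative visit. For slit lamp, "The listing will include all slit-lamp data from all visits with the following variables"; for fundus, "The listing will include all fundus examination data from all visits with the following variables".

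Four other provisions bear on the point:

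- SAP 5.3 sets a baseline for the safety section: "Baseline will be defined as the last measurement prior to exposure to investigational product, except otherwise stated".
- SAP 5.3.10 uses it for intraocular pressure, where "observed values and change from baseline values will be presented at each study visit".
- Protocol 12.6 states: "Safety analyses will be conducted using the safety analysis set on a treatment-emergent basis". SAP 2.2 repeats this, but explains only which lens an eye is counted under.
- Protocol Table 3-1 and SAP Table 10-1 schedule both examinations at Visit 0 for both eyes. If first-eye surgery slips beyond 60 days, Protocol 7.1 lets the subject continue only if "Visit 0 biometry, tonometry, slit lamp examination, and dilated fundus exam assessments are repeated", so a current preoperative record exists.

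**The concern.** Slit-lamp and fundus examinations are two of the safety endpoints named in Protocol 12.6 and SAP 5.1. The useful safety question is how many eyes in each arm acquired a finding, or got worse, after the lens was implanted. The planned tables answer a different one: how many eyes have a finding at a visit, whenever it arose.

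Two consequences follow. A chance imbalance in findings present before surgery carries through to every postoperative visit. And an eye already abnormal on a parameter cannot register as newly abnormal on it, so a real difference between lenses is diluted. The preoperative data needed to avoid both are already collected.

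**Working it through.** **Step 1. Compare the safety items that have a Visit 0 assessment.**

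| Item | Use of preoperative information in the SAP |
|---|---|
| Adverse events | Events before exposure are listed separately (5.3.1) |
| Intraocular pressure | Change from baseline is summarized; large changes from the same eye's baseline are listed (5.3.10) |
| Slit lamp | Not used in the table; visible only in the listing (5.3.8) |
| Fundus | Not used in the table; visible only in the listing (5.3.9) |

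The treatment-emergent principle is made operational for adverse events and for lens attribution. It is not made operational for examination findings.

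**Step 2. Effect on the expected arm difference.** The documents give no abnormality rates, so there is no plan figure to reproduce, and every rate below is an assumption. Let b be the proportion of eyes with a baseline finding that persists, equal in expectation across arms because allocation is 1:1. Let q be the rate of new findings among eyes normal at baseline. The table shows

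p = b + (1 − b)q.

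The expected arm difference in p is (1 − b)(q_T − q_C). If q is equal in the two arms, it is zero. With q = 5% and 15%, a true difference of 10 points:

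- b = 5%: 0.95 × 10 = 9.5 points
- b = 10%: 0.90 × 10 = 9 points
- b = 20%: 0.80 × 10 = 8 points
- b = 40%: 0.60 × 10 = 6 points

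**Step 3. Chance noise.** Take 70 subjects per arm (the planned completers, Protocol 8), two eyes each, and an assumed between-eye correlation ρ = 0.5. If a proportion p of eyes is counted,

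SE(difference) = √[2p(1 − p)(1 + ρ)/(2 × 70)] = √[p(1 − p)(1 + ρ)/70].

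- p = 3% (a new-only count): √(0.0291 × 1.5/70) = 2.5 points
- p = 5%: √(0.0475 × 1.5/70) = 3.2 points
- p = 20%: √(0.16 × 1.5/70) = 5.9 points
- p = 30%: √(0.21 × 1.5/70) = 6.7 points

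At a common ρ, the ratio to the 3% case is √[p(1 − p)/0.0291]: 1.3 at 5%, 2.3 at 20% and 2.7 at 30%. This ignores the smaller denominator of a new-only percentage, so it slightly flatters the new-only count. The tables are per parameter. Rates of 20–30% are more like an any-abnormality total, so the lower ratio may be nearer the mark for a single parameter.

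**Step 4. What share of counted eyes is pre-existing?** The share is b/[b + (1 − b)q].

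- b = 2%, q = 40%: 0.02/(0.02 + 0.392) = 5%
- b = q = 5%: 0.05/(0.05 + 0.0475) = 51%
- b = 40%, q = 2%: 0.40/(0.40 + 0.012) = 97%

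The share can be almost anything, and the documents do not narrow it.

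**Step 5. Would a Visit 0 column suffice?** It would show the net change only. If ten eyes resolve and ten others become abnormal on a parameter, the two visit totals are identical although ten eyes have a new finding.

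**The case against.** The case for leaving the tables alone has real substance.

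- Read literally, each scheduled visit includes Visit 0, so preoperative rates by arm would sit in the same table and an imbalance at entry would be visible. This stands as a safeguard against misreading, but it gives marginal totals only (Step 5).
- The listings show Visit 0 status for every eye abnormal after surgery. New findings can therefore be recovered, but by hand and without a planned count by arm.
- Protocol 11.3 sends untoward changes that matter clinically to adverse event reporting, which is tabulated by arm. That route depends on the investigator's judgement, and Protocol 11.4 removes typical early postoperative findings expected to settle within a week.
- The general treatment-emergent statement might be meant to cover these tables. Nothing in 5.3.8 or 5.3.9 says how, and as worded they count every abnormality.
- Eligibility excludes macular degeneration and clinically significant corneal or ocular surface disease. This limits b, but findings below those thresholds remain eligible.
- The parameters and grading are on a case report form that is not in the documents, so per-parameter rates cannot be judged.

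A reader might infer that pre-existing findings dominate these tables, or that the comparison is biased toward one lens. The documents support neither. Step 4 shows that dominance depends wholly on unstated rates. It is least plausible for slit lamp at Day 1–2, when Protocol 11.4 expects new findings such as cells and flare or corneal edema. Randomization removes any expected direction.

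**Conclusion.** The point holds as a gap in reporting. The two tables do not distinguish new or worsened abnormalities from those present at Visit 0, which is out of step with the handling of intraocular pressure and adverse events and leaves the treatment-emergent statement without a rule for examination findings. The effect is dilution by (1 − b) plus chance noise, with no directional bias.

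The size is unknown. On the assumptions shown, it runs from slight (9.5 points seen for a true 10, and noise about 1.3 times larger, at 5%) to appreciable (8 points seen, and noise about 2.3 times larger, at 20%). The dilution formula assumes that baseline findings persist and that b is equal in the arms. The gap is probably clearest for fundus, which is scheduled only at Visit 0, 1 month and 3 months, and for slit lamp at the two later visits.

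The importance is minor. SAP 5.2 sets no safety hypotheses, the summaries are descriptive, and the primary noninferiority conclusion does not depend on them.

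**What to change.** In SAP 5.3.8 and 5.3.9, add for each parameter, by arm and postoperative visit:

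1. The number and percentage of eyes with a new abnormality: normal at that eye's baseline as defined in SAP 5.3, abnormal at the visit. Use as denominator the eyes normal at baseline and examined at that visit.
2. Where the case report form grades the parameter, the number of eyes abnormal at baseline that have worsened.
3. The number of eyes abnormal at baseline, shown separately.

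Add one sentence stating that this is how the treatment-emergent principle applies to examination findings. Keep the planned by-visit counts as supportive, and keep the listings.

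The cost is SAP wording, one derived baseline flag and one or two extra rows per parameter. No new data, visit or form is needed. Eyes without a recorded baseline on a parameter would have to be shown as unclassified.

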5.3.9 Dilated Fundus Examination

For each dilated fundus parameter as per the CRF, numbers and percentages of eyes that experience abnormality at each scheduled visit will be presented by treatment.

A listing will be provided which presents all eyes with an abnormality in any fundus parameter at any postoperative visit. The listing will include all fundus examination data from all visits with the following variables: treatment, subject identification number, age, sex, surgery eye (first or second implanted eye), eye (OD or OS), visit, days from surgery, and fundus parameter.

Dilated fundus abnormalities will also be summarized by toric and non-toric lenses for all eyes combined only.

5.3.10 Intraocular Pressure

Intraocular pressure (IOP) measurements will be recorded in mmHg and rounded to the nearest whole mmHg. All analyses will be presented by treatment.

Descriptive statistics (number of eyes, mean, median, SD, minimum, maximum, and two-sided 95% confidence interval) of observed values and change from baseline values will be presented at each study visit.

A listing will be provided which presents all eyes with an increase or decrease in IOP of more than 10 mmHg at any postoperative visit compared to the same eye at baseline. The listing will include the following variables: treatment, IOL model, subject identification number, age, sex, surgery eye (first or second implanted eye), eye (OD or OS), visit, days from surgery, value at the visit, baseline value, and a change from baseline value.

IOP will also be summarized by toric and non-toric lenses for all eyes combined only.

5.3.11 IOL Position Change (Tilt/Decentration)

[figure not shown]
The number and percentage of eyes with a change from last visit (per CRF) in IOL position category (Tilted ≥ 1 degree, Decentered ≥ 0.5 mm) will be presented by treatment.

In addition, a listing of eyes with any IOL position change will be provided. The listing will include the following variables: treatment, subject identification number, age, sex, surgery eye (first or second implanted eye), eye (OD or OS), visit, days from surgery, and amount of tilting or decentration.

IOL position change will also be summarized by toric and non-toric lenses for all eyes combined only.

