Reasons for discontinuation during surgery		X	X					
Slit lamp examination	X			X	X	X	X	(√)
Dilated fundus examination	X					X	X	(√)
IOP	X			X	X	X	X	(√)

	Both Eyes	First Operative Eye ¹	Second Operative Eye ¹	First Operative Eye	Second Operative Eye	Both eyes		Applicable eye
	Pre-op Visit 0	Visit 00	Visit 00A	Visit 1	Visit 1A	Visit 2A	Visit 3A/Exit Visit	Unscheduled visit
		Day 0	Day 0A	Day 1-2	Day 1-2	Day 30-60 (1month)	Day 90-120 (3months)	N/A
IOL position change (tilt and decentration)				X	X	X	X	(√)

NOTES:

- 1 It is recommended that Visit 00 (1st eye surgery) occur within 0 to 30 calendar days after the Preoperative Visit (Visit 0). Visit 00A (2nd eye surgery) may have the option to occur same day as Visit 00 (1st eye surgery) and it is recommended that the 2nd eye surgery occur within 14 days after the 1st eye surgery.
- 2 CRF data will be targeted:
 - Medical History: All ocular history, targeted systemic history within 30 days prior to screening visit
 - Concomitant medications: All ocular medications, targeted systemic medications within 30 days prior to screening visit
- 3 In women of childbearing potential only.
- 4 Preoperative pupil size is the ability to constrict with a penlight.
- 5 It is recommended that randomization occur within 14 days prior to 1st eye surgery.

(√) Assessment performed as necessary

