10.2.10 Slit lamp Examination: Safety Assessment

Slit lamp examination must be performed in both eyes. This assessment must be performed by a delegated investigator. Record any slit lamp findings, IOL Position Change (Tilt and Decentration), any IOL Observations, and any Subjective PCO including Posterior Capsulotomy. Refer to MOP for details.

For toric IOLs only: Record the actual axis of IOL orientation at implantation, and at subsequent visits. This assessment must be performed by a delegated investigator.

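### SAP 5.3.11 counts lens tilt and decentration only against the last visit and leaves the thresholds and the Visit 1/1A reference undefined, so some displaced eyes may go uncounted

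*SAP*

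**What the plan says.** Tilt and decentration form a named safety endpoint in both documents (Protocol 6.5 and 12.6; SAP 5.1).

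- **Tabulation.** SAP 5.3.11 gives, by treatment, a count and percentage for "eyes with a change from last visit (per CRF) in IOL position category (Tilted ≥ 1 degree, Decentered ≥ 0.5 mm"). It also splits the summary by toric and non-toric lenses.
- **Listing.** The same section says that "a listing of eyes with any IOL position change will be provided". No threshold is attached. The variables include "visit, days from surgery, and amount of tilting or decentration".
- **Schedule.** In Protocol Table 3-1 and SAP Table 10-1 the item is marked at Visits 1/1A, 2A and 3A, and as needed at unscheduled visits. It is not marked at the operative visits. Protocol 7.1 places "Visit 1/1A (Days 1-2) after 1st and 2nd eye surgery respectively"; Visit 2A falls on Days 30-60 and Visit 3A on Days 90-120 after the second surgery.
- **Recording.** Protocol 10.2.10 instructs: "Record any slit lamp findings, IOL Position Change (Tilt and Decentration), any IOL Observations, and any Subjective PCO including Posterior Capsulotomy". It refers to the Manual of Procedures for detail. For toric lenses it adds: "Record the actual axis of IOL orientation at implantation, and at subsequent visits". That covers rotation, not tilt or decentration.

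No section defines the reference for Visit 1/1A, and none plans a table of tilt or decentration status by visit or of change from a fixed point.

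**The concern.** A rolling reference answers whether the lens moved since it was last examined. It need not answer whether the lens is out of position, or how far it has moved in total. Two patterns are at risk: slow drift in steps that each stay below the cut-off, and a lens already displaced at the first postoperative examination that then stays put.

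The SAP summarises comparable safety findings without a rolling reference. Posterior capsule opacification uses the maximum rating during the study (5.3.4), slit-lamp findings are tabulated at each visit (5.3.8), and IOP uses observed values and change from baseline (5.3.10). The general safety baseline in SAP 5.3, the last measurement before exposure to the product, cannot exist for the position of an implanted lens, so it does not fill the gap.

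At stake is the by-treatment rate of tilt and decentration for two lenses with different haptic designs (Protocol Tables 9-1 and 9-2). The table could show no position change for an eye whose final position is beyond the plan's own cut-off.

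**Working it through.** The plan gives no expected rate, power or other figure for this endpoint, so there is nothing to reproduce. The check is one of logic, using illustrative lens paths that are assumed and not taken from the documents.

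**Inputs from the documents**
- Thresholds: tilt 1 degree, decentration 0.5 mm (SAP 5.3.11).
- Scheduled assessments per eye: Visit 1 or 1A, Visit 2A, Visit 3A (Protocol Table 3-1; SAP Table 10-1).

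**Step 1. Largest uncounted drift if the thresholds mean size of change**
- Three scheduled assessments give 3 − 1 = 2 intervals from Visit 1/1A to Visit 3A.
- Ceiling = number of intervals × threshold, approached from below.
- Decentration: 2 × just under 0.5 mm = just under 1.0 mm.
- Tilt: 2 × just under 1 degree = just under 2 degrees.
- Examples: 0.4 + 0.4 = 0.8 mm, above 0.5 mm, with neither step reaching it; 0.9 + 0.9 = 1.8 degrees, above 1 degree, with neither step reaching it.

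**Step 2. The four readings the text allows**

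Two things are undefined: what the thresholds mean, and what Visit 1/1A is compared with. The drift path starts at zero at Visit 1/1A and moves 0.4 mm (or 0.9 degree) per interval. The stable path is 0.8 mm (or 3 degrees) from Day 1-2 onward.

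| Thresholds mean | Reference at Visit 1/1A | Drift counted? | Stable early displacement counted? |
|---|---|---|---|
| Size of change | None | No | No |
| Size of change | Surgery | No | Yes |
| Shift in category | None | Yes | No |
| Shift in category | Surgery | Yes | Yes |

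Three of the four readings miss at least one pattern. In the third, a lens that is already over the cut-off and gets worse is missed as well: 0.6 mm moving to 1.4 mm (illustrative) stays in the same category throughout.

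**Step 3. The listing**

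It has no threshold, so on its wording a drifting eye could appear with its steps. It requires a change, so an eye recorded as unchanged may not appear. The section does not say whether the amount listed is a change or a position, and the listing gives no rate by treatment.

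**Step 4. The same paths under fixed criteria**
- Status at each visit: drift is counted at Visit 3A (0.8 ≥ 0.5 mm; 1.8 ≥ 1 degree), and stable displacement from Visit 1/1A onward (0.8 ≥ 0.5 mm; 3 ≥ 1 degree).
- Maximum change from Visit 1/1A: drift is counted (0.8 mm; 1.8 degrees). Stable displacement is not, which is why both criteria are needed.

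**The case against.** The best defence is that the natural reading is sound. Tilted and decentered read as states with cut-offs, so a change of category would catch drift once the lens crosses the line. The item is scheduled at Visit 1/1A, where it would mean little without a reference, and the preceding visit for that eye is surgery. On those two readings together nothing in the table above is missed.

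Other outputs also help. The listing covers any change. IOL observations and slit-lamp abnormalities are tabulated at each visit (SAP 5.3.3, 5.3.8). Lens dislocation must be reported as a serious adverse event (Protocol 11.1), and secondary surgical interventions are tabulated and listed (SAP 5.3.1). The CRF and Manual of Procedures, which were not available, may settle the definitions.

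Much of this stands, and it is why the point is conditional and minor. It does not close the gap. The favourable combination is one of four, and it needs a tilt and decentration reference at surgery that neither schedule marks; only toric axis is recorded at implantation. The other outputs make a serious displacement less likely to go unseen, but none is stated to give a rate of tilt or decentration by treatment.

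A reader might go further and infer three things that the documents do not support:
- **That the endpoint certainly misses these eyes.** Each miss depends on a reading the text leaves open.
- **That the drift ceiling is higher, because the step from surgery to Visit 1/1A adds an interval.** That step exists only if surgery is the reference, and with that reference the early displaced eye is counted. The larger ceiling and the missed early displacement cannot both hold.
- **That the CRF records only whether position changed.** The listing variable for the amount of tilt or decentration suggests that amounts are captured.

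**Conclusion.** The point holds in conditional form and is minor. SAP 5.3.11 uses a rolling reference and leaves two definitions open. If the thresholds mean size of change, sub-threshold drift of up to just under 1.0 mm or 2 degrees between Visit 1/1A and Visit 3A is never counted in the by-treatment table. If Visit 1/1A has no earlier reference, a lens displaced at Day 1-2 and stable afterwards is not counted under either meaning.

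These statements assume scheduled visits only and that the CRF and Manual of Procedures do not settle the definitions. The step sizes are illustrative. The documents give no tilt or decentration rate, so the number of eyes affected is unknown; it is probably small, and no count per arm can be supported. The endpoint is descriptive (SAP 5.2), and the primary noninferiority analysis is unaffected.

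**What to change.** In SAP 5.3.11:

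1. State what position at Visit 1/1A is compared with.
2. State whether the 1 degree and 0.5 mm thresholds refer to the size of a change or to the state of the lens.
3. Add, by treatment, the number and percentage of eyes meeting either threshold (a) at each postoperative visit and (b) by maximum change from Visit 1/1A at any later visit. Use the amounts recorded at the slit-lamp examinations already scheduled.
4. List any eye meeting (a) or (b), as well as any eye with a change.
5. Confirm that the CRF captures position as well as change, and clarify the field if it does not.

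The cost is a paragraph of SAP text, one extra descriptive table and at most a CRF clarification. No visit, examination or sample size changes. Reported rates may be slightly higher than under the present rule.
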